8.3 Required Concomitant Medications and Procedures

Not applicable.

9 STATISTICAL CONSIDERATIONS

Detailed methodology for summary and statistical analyses of the data collected in this study will be documented in a Statistical Analysis Plan (SAP), which will be maintained by the sponsor. The SAP may modify the plans outlined in the protocol; however, any major modifications of the key endpoint definitions and/or its analysis will also be reflected in a protocol amendment.

9.1 Overview

This is a Phase 3, open-label, multicenter extension study to evaluate the safety and efficacy of ozanimod in subjects with moderately to severely active CD, defined as a CDAI score of ≥ 220 to ≤ 450 . It is anticipated that approximately [REDACTED] subjects who participated in prior studies of ozanimod in CD will be eligible for treatment in this study

9.2 Study Population Definitions

All subjects who receive at least 1 dose of IP will comprise both the Intent-to-Treat (ITT) population and the Safety population. These populations will be used to summarize all safety and efficacy data, respectively.

9.3 Sample Size and Power Considerations

As this is an Open-label Extension Study for subjects who participated in a prior study of ozanimod for CD, there is no statistical basis for the sample size. It is anticipated that approximately [REDACTED] subjects who participated in prior studies of ozanimod in CD will be eligible for treatment in this study.

9.4 Background and Demographic Characteristics

Subject demographics and baseline characteristics from RPC01-3201, RPC01-3202, and RPC01-2201 will define subject demographics and baseline characteristics for RPC01-3204. Descriptive summaries will be presented for the safety and efficacy variables collected. Continuous variables will be summarized using number of subjects (n), mean, standard deviation (SD), median, minimum, and maximum. Categorical variables will be summarized using frequency counts and percentages.

Subject demographics and baseline characteristics will include age, sex, race, ethnicity, height, weight, body mass index, age at CD symptom onset, age at CD diagnosis, years since CD symptom onset, years since CD diagnosis, baseline CDAI score, baseline SES-CD score, baseline abdominal pain and stool frequency, prior anti-TNF use, and prior corticosteroid use.

Subject baseline for a given assessment is defined as the most recent non-missing measurement for that assessment immediately prior to administration of the first dose of IP (or ozanimod for safety analysis) for that subject across all of the following studies: RPC01-3201, RPC01-3202, RPC01-3203, RPC01-3204, and RPC01-2201. Additional details are provided in the SAP.

9.5 Subject Disposition

Subject disposition will include, at the minimum, the following:

- the number of subjects enrolled
- the number of subjects dosed
- subject status including completion of prior study
- the number of subjects completing the RPC01-3204 Study
- the number of subjects not completing the RPC01-3204 Study by reason for dropout

9.6 Efficacy Analysis

Due to the open-label nature of the study and the lack of a control group, all data will be summarized, and no hypothesis testing will be performed. Each efficacy endpoint will be summarized and [REDACTED] around the estimates may also be presented. All efficacy data will be listed.

For all proportion-based efficacy endpoints, subjects with missing efficacy data will be considered non-responders.

For continuous efficacy endpoints, subjects with missing data will have their last post-baseline value carried forward.

Observed-cases analyses will also be presented for all efficacy endpoints.

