1.3 Study Rationale

Given the mechanism of action of ozanimod, data from the preclinical animal model, the positive results from the Phase 2 UC study, RPC01-202, and preliminary results from the Induction Period

of the Phase 2 study in CD, RPC01-2201, a Phase 3 program with ozanimod in CD is being conducted.

The current study is designed to assess the long-term safety and explore long-term efficacy of ozanimod in subjects with moderately to severely active CD. This study will allow subjects who are receiving clinical benefit from ozanimod the opportunity to continue to receive IP and experience potential long-term endoscopic benefit. For subjects who are not in clinical response and/or clinical remission after completing 12 weeks in the Induction Studies, this study provides an opportunity for potential delayed clinical benefit.

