2 STUDY OBJECTIVES AND ENDPOINTS

2.1 Study Objective

- Demonstrate the long-term safety and explore long-term efficacy of ozanimod for the treatment of subjects with moderate to severely active CD.

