4.2 Inclusion Criteria

Subjects must satisfy the following criteria to be enrolled in the study:

[figure not shown]
1. Subjects who are not in clinical response and/or clinical remission after completing 12 weeks in the Induction Studies RPC01-3201 or RPC01-3202, subjects who experience relapse in the Maintenance Study RPC01-3203, subjects who complete the Maintenance Study RPC01-3203, subjects who complete at least 1 year of RPC01-2201.
2. Subject should not have any constraints under local regulations, must provide written informed consent prior to any study-related procedures, and must have the ability to comply with the [REDACTED]
3. Female subjects of childbearing potential (FCBP):

Note: For the purposes of this study, a female subject is considered to be of childbearing potential if she 1) has not undergone a hysterectomy (the surgical removal of the uterus) or bilateral oophorectomy (the surgical removal of both ovaries) or 2) has not been postmenopausal for at least 24 consecutive months (that is, has had menses at any time during the preceding 24 consecutive months).

Must agree to practice a highly effective method of contraception throughout the study until completion of the [REDACTED] Safety Follow-up Visit. Highly effective methods of contraception are those that alone or in combination result in a failure rate of a Pearl Index of less than 1% per year when used consistently and correctly. Examples of acceptable methods of birth control in the study are the following:

- combined hormonal (containing oestrogen and progestogen) contraception, which may be oral, intravaginal, or transdermal
- progestogen-only hormonal contraception associated with inhibition of ovulation, which may be oral, injectable, or implantable
- placement of an intrauterine device (IUD)
- placement of an intrauterine hormone-releasing system (IUS)
- bilateral tubal occlusion
- vasectomized partner
- complete sexual abstinence

Periodic abstinence (calendar, symptothermal, post-ovulation methods), withdrawal (coitus interruptus), spermicides only, and lactational amenorrhoea method are not acceptable methods of contraception. Female condom and male condom should not be used together.

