9.7 Safety Analysis

Adverse events will be monitored during the study and the data analyzed with respect to incidence within each parent study treatment group as well as severity and potential relationship of the AEs to IP.

All AEs with a start date before the first open-label dose date, and that are ongoing from a previous study to this Open-label Extension Study, will be listed in the AE data listing and labeled as “Prior Adverse Event.”

Adverse events with an onset date on or after the first dose of drug in this study, or with an onset prior to the first dose of IP that increase in severity on or after the first dose of IP, will be considered treatment emergent. Treatment-emergent AEs will be summarized for the Safety population by system organ class and preferred term and presented in descending order of frequency within each System Organ Class. Serious AEs and AEs leading to discontinuation will be summarized similarly. Adverse events will be summarized by patient years of exposure (PYE).

Associated laboratory parameters such as hepatic profile, renal function, and hematology values will be grouped and presented together. Individual subject values will be listed and values outside of the standard reference range will be flagged. Shift tables will be produced showing the frequency of shifts from baseline to the highest and to the lowest on-study value in and out of the normal range as well as by visit. Changes from Baseline to each visit for each laboratory parameter will also be summarized.

The change from baseline to each visit for each of the vital sign variables will be summarized. Abnormal vital sign values will be flagged and listed.

The change from baseline to each visit for each of the ECG parameters will be summarized. An outlier analysis of ECG results will be conducted.

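### Must Section 9.6 split efficacy by entry route and parent-study treatment, given that 9.7 already groups adverse events by parent treatment?

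*Combined protocol and SAP*

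**What the plan says.** Section 9.6 states "Each efficacy endpoint will be summarized and" then continues, around a redaction, that something may also be shown around the estimates. The position of the redaction suggests a measure of precision rather than a subgroup. The section rules out hypothesis testing, counts missing data as non-response for proportions, carries the last value forward for continuous endpoints, adds observed-case analyses and promises listings of all efficacy data.

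Section 9.2 puts every dosed subject into both the ITT and the Safety population and adds: "These populations will be used to summarize all safety and efficacy data, respectively".

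Section 4.2 sets the entry routes. The first is "Subjects who are not in clinical response and/or clinical remission after completing 12 weeks in the Induction Studies RPC01-3201 or RPC01-3202". The others are "subjects who experience relapse in the Maintenance Study RPC01-3203, subjects who complete the Maintenance Study RPC01-3203, subjects who complete at least 1 year of RPC01-2201".

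Section 1.3 describes what the study offers subjects. For those doing well: "This study will allow subjects who are receiving clinical benefit from ozanimod the opportunity to continue to receive IP". For induction non-responders: "this study provides an opportunity for potential delayed clinical benefit". The efficacy part of the objective in Section 2.1 is only to "explore long-term efficacy of ozanimod".

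Section 9.7 analyses adverse events by "incidence within each parent study treatment group". Section 9 defers detailed methodology to a SAP, and Section 9.4 points there again.

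**The concern.** Two of the four routes (induction non-response and maintenance relapse) are defined by a poor outcome. The other two are defined by completion or by at least a year of treatment. The same endpoint therefore carries different meanings. Under Section 9.4 the efficacy baseline is the last value before the first IP dose in any of the studies. A maintenance completer may already meet a CDAI-reduction endpoint on Day 1, whereas for an induction non-responder meeting it would generally be a new event. An overall rate answers neither of the questions suggested by Section 1.3.

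Prior exposure may differ as well. Section 9.4 separates first IP from first ozanimod, and Section 15.2 protects the parent-study blind. Some induction non-responders may therefore be receiving ozanimod for the first time, and a later response in them would not be delayed benefit. This is an inference; the protocol does not state it for the induction studies.

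Section 9.7 shows that the sponsor regards parent treatment as relevant and will hold the variable, so its absence from 9.6 looks like an oversight. What is at stake is how the annual efficacy results are read, and whether a split might be chosen only after the data are seen.

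**Working it through.** The plan states no figure to reproduce: the number of subjects is redacted, and Section 9.3 says the sample size has no statistical basis.

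**1. Does one population mean one column?** Section 9.2 gives safety and efficacy the same set of subjects. Section 9.7 nevertheless breaks adverse events down by parent treatment group. So 9.2 fixes who is analysed and leaves the table layout open. Section 9.6 is silent on columns; it does not prescribe a single overall rate.

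**2. Can the split be made later without bias in its definition?** Route is settled by inclusion criterion 1, and parent assignment precedes entry. Both are therefore fixed before the first dose here. Parent treatment is needed for 9.7, prior-study status is reported under 9.5, and efficacy data are listed under 9.6. No new data are required, and outcomes leave little room to shape the groups.

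**3. How much does an overall rate say about induction non-responders?** Let P be the overall rate, w their share, q their rate and r the rate in all others, so that P = wq + (1 − w)r. With only P and w known, q lies between max(0, (P − (1 − w))/w) and min(1, P/w). For P = 30% (assumed):

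| w (assumed) | lower limit of q | upper limit of q |
|---|---|---|
| 30% | 0% | 0.30/0.30 = 100% |
| 50% | 0% | 0.30/0.50 = 60% |
| 70% | 0% | 0.30/0.70 = 42.9% |
| 90% | (0.30 − 0.10)/0.90 = 22.2% | 0.30/0.90 = 33.3% |

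The limits are correct, but they hold for any subgroup with the same share. At w = 50% the extremes need r = 0% or r = 60% in everyone else. They illustrate what pooling hides in general and are not evidence about this trial.

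**4. Can the mix of routes drift over time?** Take q = 0% (assumed) and r = 65.6%. The latter is the higher of the two remission figures for RPC01-2201 in Section 1.2.2.2, read as Week 52 and applied to all other routes as an assumption. Start with 100 subjects, 50 of them induction non-responders.
- Overall rate: 0.50 × 65.6% = 32.8%.
- Suppose non-responders leave until they are 20% of those observed, which leaves 12.5 of them with the 50 others. Observed-case rate: 32.8/62.5 = 52.5%.
- With missing counted as non-response, the denominator stays at 100 and the rate stays at 32.8/100 = 32.8%.

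The drift affects only the observed-case analysis. The missing-as-non-response rate prescribed in 9.6 is not inflated by it, and the gap between the two displays would reveal it.

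**5. What would mandatory columns cost?** There are 13 efficacy endpoints in Section 2.2.1, about 5 annual evaluations (264/52 = 5.1) and two displays (imputed and observed cases). That is 13 × 5 × 2 = 130 estimates per added column. The 95% Wilson half-width is z/(1 + z²/n) × √(p(1 − p)/n + z²/(4n²)), with z = 1.96. At p = 30% and n = 20 this is 1.644 × 0.1136 = 18.7 points. It is 12.3 points at n = 50, 8.8 at n = 100 and 4.0 at n = 500 (all n assumed).

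**The case for a change.** The strongest case for a change is that exploring long-term efficacy means little unless delayed and maintained benefit can be told apart, and that the tables cost almost nothing because the variables exist. Section 3.2 also lets the sponsor end the study early once long-term safety and efficacy have been shown, so the efficacy summaries may inform a decision. A split written down in advance is more credible than one added later in an open-label study.

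Part of this stands. Results by route would be more informative, and a reader of the eventual report should want them. But Section 1.3 describes opportunities offered to subjects. It does not set estimands, and none of the 13 endpoints is defined as delayed or maintained response by route. The comparison with 9.7 supports grouping by parent treatment only; no analysis section groups by entry route. Pre-specification protects little where nothing is tested and the groups are fixed before dosing. The early-termination clause states no efficacy threshold that an overall rate could wrongly trigger.

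A mandated split would also raise questions of its own. Subjects from RPC01-3203 may have both an induction and a maintenance assignment, and someone must decide which counts as parent treatment. A minimum cell size would be needed too, with the number of subjects redacted. These are table-specification decisions of the kind that Section 9 leaves to the SAP.

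**Conclusion.** The observation is accurate: Section 9.6 names no efficacy breakdown, while Section 9.7 names one for adverse events. It is missing detail that analysts can fill sensibly, and the SAP may already fill it. The rate over all dosed subjects is a valid description of that population, and the protocol does not confine the report to it. Adding columns would leave the number of subjects, every error rate and every stated figure as they are.

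The size of any loss cannot be computed, because the enrolment, the share by route and the route-specific rates are not given. The 0% to 60% range rests on an assumed overall rate and an assumed share. The conclusion relies on two things: that route and parent assignment are retained in the data, as 9.5 and 9.7 imply, and that the efficacy results remain descriptive. If the SAP proved silent as well, the consequence would be a less informative first set of tables, recoverable from data already held.

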2.2 Study Endpoints

Note: Endpoints will be evaluated annually for up to 264 weeks.

2.2.1 *Efficacy Endpoints:*

- Proportion of subjects with a CDAI score of < 150
- Proportion of subjects with a SES-CD decrease from baseline of $\geq 50\%$
- Proportion of subjects with average daily abdominal pain score ≤ 1 point, and average daily stool frequency ≤ 3 points with abdominal pain and stool frequency no worse than baseline
- Proportion of subjects with CDAI reduction from baseline of ≥ 100 points or CDAI score of < 150
- Proportion of subjects with absence of ulcers ≥ 0.5 cm with no segment with any ulcerated surface $\geq 10\%$
- Proportion of subjects with CDAI reduction from baseline of ≥ 70 points
- Change from baseline in CDAI
- Proportion of subjects with CDAI reduction from baseline of ≥ 100 points or CDAI score of < 150 and SES-CD decrease from baseline of $\geq 50\%$
- Proportion of subjects with CDAI score of < 150 and SES-CD ≤ 4 points and a SES-CD decrease ≥ 2 points
- Proportion of subjects with average daily abdominal pain score ≤ 1 point and average daily stool frequency ≤ 3 points with abdominal pain and stool frequency no worse than baseline and SES-CD ≤ 4 points and a SES-CD decrease ≥ 2 points
- Proportion of subjects with SES-CD ≤ 4 points and a SES-CD decrease ≥ 2 points
- Proportion of subjects with a CDAI score < 150 in subjects off corticosteroids
- Proportion of subjects with a Crohn's Disease Endoscopic Index of Severity (CDEIS) decrease from baseline of $\geq 50\%$

2.2.3 *Overview of Safety Assessments*

The incidence, severity, relationship, and type of treatment-emergent adverse events (TEAEs), serious adverse events (SAEs), and AEs leading to discontinuation of IP will be summarized (see [Section 14](#)), as well as clinically meaningful changes from baseline for clinical laboratory measures, vital signs, and electrocardiograms (ECGs). [REDACTED]

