8.1 Permitted Concomitant Medications and Procedures

Any medication that is considered necessary for the subject's health and that is not expected to interfere with the evaluation of or interact with IP may be continued during the study. All treatments being taken in addition to the IP by the subjects on entry to the study or at any time during the study are regarded as concomitant treatments and must be documented on the appropriate section of the eCRF. All prior medications that were continuing at the time of study discontinuation in the prior study or any new medications that started between the prior study discontinuation and enrollment in RPC01-3204 need to be documented.

The decision to temporarily interrupt dosing for treatment of an intercurrent medical condition, or for major surgery that could present an unreasonable risk to the subject, remains the responsibility of the treating physician, which will not be delayed or refused by the Sponsor. Prior to interruption of dosing, the Investigator may contact the Medical Monitor and forward appropriate supporting documents for review and discussion. The Investigator will report the action taken with IP. The Medical Monitor should be contacted to discuss treatment re-initiation ([Section 7.2.1](#)). See [Section 14](#) for permanent discontinuation of IP.

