8.1.1 Corticosteroid Taper

If subjects are still receiving corticosteroids in the Open-label Extension Study, subjects should begin tapering corticosteroids once clinical response or clinical remission has been achieved.

8.1.2 *Aminosalicylates or Purified Medicinal Probiotics*

Subjects receiving 5-aminosalicylic acid (ASA) or purified medicinal probiotics should maintain a stable dose throughout the study unless reduction or discontinuation is clinically indicated.

[figure not shown]
8.1.3 *COVID-19 Vaccination*

COVID-19 vaccines that are NOT live are allowed and should be handled in the same manner as other vaccines. Administration may occur during the study, including during treatment with IP and after the last dose of IP.

Non-live COVID-19 vaccination is considered a simple concomitant medication within the study. However, the efficacy and safety of non-live vaccines (including non-live COVID-19 vaccines) in subjects receiving ozanimod is unknown. The individual benefit/risk assessment of a vaccine remains with the Investigator. If the assessment of the Investigator suggests the vaccine to be beneficial, it must be a non-live, replication incompetent vaccine, and be approved or otherwise authorized (eg, Emergency Use Authorization [FDA] or equivalent) by national health authorities.

See [APPENDIX B](#) for further SARS-CoV-2 guidance.

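### As visible, Section 9.6 has no rule for new or increased corticosteroids or added Crohn's therapy, so on 11 of 12 proportion endpoints a subject who meets the threshold after such treatment counts as an ozanimod responder

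*Combined protocol and SAP*

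**What the plan says.** Section 9.6 sets out how efficacy data are handled. For binary endpoints the rule is: "For all proportion-based efficacy endpoints, subjects with missing efficacy data will be considered non-responders". For continuous endpoints: "For continuous efficacy endpoints, subjects with missing data will have their last post-baseline value carried forward". It adds: "Observed-cases analyses will also be presented for all efficacy endpoints". None of the three mentions concomitant CD treatment. The analysis is descriptive, since "no hypothesis testing will be performed", and Section 9.3 says that "there is no statistical basis for the sample size".

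Corticosteroids are in use in the study. Section 8.1.1 says of subjects still receiving them that "subjects should begin tapering corticosteroids once clinical response or clinical remission has been achieved". The visible text covers tapering only and says nothing about starting or increasing them. Section 8.1 requires documentation of "All treatments being taken in addition to the IP by the subjects on entry to the study or at any time during the study", and Section 8 asks for dose, dates and reason for use.

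One endpoint in Section 2.2.1 takes account of corticosteroids: "Proportion of subjects with a CDAI score < 150 in subjects off corticosteroids".

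**The concern.** A subject may flare on ozanimod, be given corticosteroids or have them increased, continue ozanimod, and be below the threshold at the next annual evaluation. The score is not missing, so the only stated override does not apply, and the subject enters the numerator.

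The event is plausible here. Section 4.2 admits subjects without response or remission after induction and subjects who relapsed in maintenance. Treatment may last 264 weeks. Section 14.2 leaves stopping for lack of efficacy to the decision of the subject and/or the investigator, so the visible text does not force a flaring subject off ozanimod.

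With no control arm, the annual proportions are the efficacy result. Response that depends on added treatment would be reported as long-term ozanimod response. Section 3.2 also lets the sponsor stop the study early if it judges the objectives on long-term safety and efficacy to be met, so these rates may inform a decision.

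**Working it through.** **No design figure to reproduce.** The study has no test, no power statement and no derived sample size, and the planned number of subjects is redacted. The check is a count of endpoints, a reading of the rules, and an illustration of size.

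**1. Count of endpoints (Section 2.2.1).** There are 13 efficacy endpoints. One is continuous (change in CDAI), which leaves 13 − 1 = 12 proportions. One of these names corticosteroids, which leaves 12 − 1 = 11 without such a condition:
- 4 rest on symptoms or CDAI alone: CDAI below 150; the abdominal pain and stool frequency criterion; the 100-point CDAI response; the 70-point CDAI response.
- 7 need endoscopy: SES-CD halving; the ulcer criterion; CDAI response with SES-CD halving; CDAI remission with low SES-CD; the pain and stool criterion with low SES-CD; low SES-CD alone; CDEIS halving.

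**2. Classification under the visible text.** Take a subject on ozanimod with new or raised corticosteroids and a non-missing score.
- Score fails the threshold: non-responder on every endpoint.
- Score meets the threshold, one of the 11 endpoints: responder.
- Score meets the threshold, off-corticosteroid endpoint: not a responder. The text does not say whether the subject fails or leaves the denominator. A subject given a different CD therapy and no corticosteroids would still count here.

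The observed-cases analysis has the same numerator and a denominator that is no larger, so the gap in percentage points is at least as large there.

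**3. Size.** Let r be the share of subjects on newly started or raised corticosteroids (or added CD therapy) at the evaluation, and p the share of those who meet the threshold. Then

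rate under present rule − rate under a failure rule = r × p.

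Neither r nor p is in the documents. Assumed ranges are r from 5% to 20% and p from 30% to 60%:
- Low: 0.05 × 0.30 = 1.5 points
- Middle: 0.10 × 0.40 = 4.0 points (a 30% rate would be reported as 34%)
- High: 0.20 × 0.60 = 12.0 points

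**4. Why r × p is an upper bound.** Let p0 be the share of the same subjects who would have met the threshold without the added treatment. The part due to that treatment is r × (p − p0). It equals r × p if p0 = 0 and is zero if p0 = p. The value of p0 is unknown.

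**5. Endoscopic endpoints.** The only endoscopic response rates in the documents are the Phase 2 figures in Section 1.2.2.2, 28.6% and 26.7%. They come from a different population and do not measure p, but both lie below the assumed floor of 30%. Putting 26.7% in for p gives 0.05 × 0.267 = 1.3 points to 0.20 × 0.267 = 5.3 points.

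**6. Sensitivity to the assumption.** The same gap can be written P × s, where P is the reported rate and s the share of apparent responders with added treatment. Taking the two Phase 2 clinical remission rates in Section 1.2.2.2 as P, and assuming s from 5% to 30%:
- P = 46.3%: 0.463 × 0.05 = 2.3 points to 0.463 × 0.30 = 13.9 points
- P = 65.6%: 0.656 × 0.05 = 3.3 points to 0.656 × 0.30 = 19.7 points

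The spread shows how strongly the answer depends on an input that the documents do not give.

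**The case against.** **The rule may exist elsewhere.** Section 9 leaves detailed methods to the SAP and allows the SAP to modify the protocol. No SAP text was supplied, and a treatment-failure rule is the kind of detail a SAP would hold. A reader might infer that the study has no such rule at all; the documents do not support that. What can be said is that Section 9.6, as visible, is silent.

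**Treatment rules may be in removed text.** The visible protocol goes from Section 8.1.3 to Section 8.3, and language on discontinuing subjects according to CDAI appears to have been taken out of the public version. How often a subject flares, receives added treatment and stays on ozanimod therefore cannot be judged. This stands as to frequency. It does not answer classification, because a breach of a prohibition does not make a score missing.

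**Added corticosteroids do not by themselves make a responder.** A reader might infer that missing data are the only route to non-response, or that every endpoint is affected. Neither is so: the threshold must still be met, and the off-corticosteroid endpoint excludes such subjects.

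**It is a choice of estimand.** Counting observed status whatever else was given is a recognised treatment-policy approach, and the study only explores efficacy. That is fair, and it is why the present rule should stay in the report. But Section 9.6 does not say that it makes this choice, and without a control arm the result describes ozanimod plus whatever was added.

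**The size is unanchored.** This stands. A reader might take 1.5 to 12 points as the bias; it is a bound under assumed inputs.

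**Conclusion.** The point holds in limited form. As visible, Section 9.6 assigns non-response only for missing data and says nothing about new or increased corticosteroids or added CD therapy during ozanimod treatment. On 11 of 12 proportion endpoints a subject who meets the threshold after such treatment is credited to ozanimod. Relative to a rule that counts added therapy as failure, the annual rates can only be equal or higher.

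The illustrative upper bound is 1.5 to 12 percentage points, resting on assumed r of 5% to 20% and p of 30% to 60%. The part caused by the added treatment is smaller to the extent that some of these subjects would have responded anyway, and p may be lower for the 7 endpoints that need endoscopy. No test or error rate is affected; what is affected is the meaning of nearly every reported efficacy proportion. The conclusion is conditional on the SAP and any Section 8.2 text, which were not seen. The change should be made, but it is not critical to the study.

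**What to change.** If the SAP already has a treatment-failure rule, cite it in Section 9.6. If not, add one paragraph to Section 9.6 and the SAP. For each proportion endpoint, a subject is a non-responder at an annual evaluation if, at that evaluation or within a set window before it, they are receiving either of the following:
- corticosteroids for CD that were started, or raised above the Day 1 dose, after the first dose in this study;
- another newly added CD therapy from a list named in the SAP.

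Fix the length of the window and the list in the SAP before database lock. Report the present rule, observed status regardless of added therapy, alongside, so that the reader sees both rates and the gap between them.

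This changes the analysis only, not who may receive treatment. The data are already collected, since Section 8 requires dose, dates and reason for each concomitant medication. The cost is a little more programming and slightly lower reported response rates. Corticosteroids unchanged since Day 1 would still be allowed under this rule, so it does not isolate ozanimod completely.
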